## **PILOT STUDY SYNOPSIS**

### **Title**

A pilot study assessing the feasibility of a randomized controlled trial evaluating aspirin versus low-molecular-weight heparin (LMWH) and aspirin in women with antiphospholipid syndrome and pregnancy loss

### **Protocol Version**

Version 4, November 7, 2017

### **Timeline**

November 2017 - October 2019

---

### **Purpose of Pilot Trial**

The purpose of this pilot trial is to determine the feasibility of conducting a multicenter randomized trial evaluating antepartum prophylaxis with aspirin versus LMWH/aspirin in women with confirmed APS and a history of late or recurrent early pregnancy loss.

### **Purpose of Full Trial:**

The purpose of the full trial is to determine the efficacy and safety of antepartum prophylaxis with aspirin alone to improve the live birth rate in women with confirmed APS and a history of late or recurrent early pregnancy loss, compared to the standard of care regime of LMWH/aspirin prophylaxis.

---

### **Pilot Trial Endpoints**

The primary feasibility outcome is the mean recruitment rate per center per month, calculated over 24 months. The secondary feasibility outcomes are: (defined in section 2.2)

1. Proportion of sites requiring >18 months to obtain all required approvals/contracts from time of delivery of all study documents
2. Proportion of screened patients who meet eligibility criteria
3. Proportion of eligible subjects who provide consent
4. Proportion of withdrawals/loss to follow-up among randomized patients
5. Proportion of subject crossover between study arms
6. Rate of compliance with antepartum LMWH use
7. Reasons for physician and patient non-consent

### **Full Trial Endpoints (Will be collected in the Pilot APPLE Trial)**

The primary full trial outcome is the live birth rate. The secondary full trial outcomes are: (defined in section 2.3)

1. Livebirth rate according to central laboratory test results
2. Pregnancy loss by gestational age (<10 weeks, 10-19 weeks, ≥20 weeks)

3. Pre-eclampsia
4. Early onset pre-eclampsia
5. Severe pre-eclampsia
6. Small-for-gestational age (SGA) <10th percentile
7. SGA <5th percentile
8. SGA <3rd percentile
9. Placental abruption requiring delivery
10. Pre-term delivery <37 weeks gestation
11. Symptomatic venous thromboembolism (VTE)
12. Symptomatic arterial thromboembolism (ATE)
13. Major bleeding
14. Clinically relevant non-major bleeding
15. Peripartum major bleeding
16. Peripartum minor bleeding
17. Non-major non-CRNM bleeding
18. Heparin induced thrombocytopenia (HIT)
19. Symptomatic fracture
20. Allergic reaction
21. All-cause mortality

---

### **Trial Design/Methodology**

The APPLE pilot trial is a feasibility study that is a multicentre, open-label, randomized controlled trial. Pregnant women with antiphospholipid syndrome (APS) and a history of late ( $\geq 10$  weeks gestation) or recurrent early ( $2 < 10$  weeks) pregnancy loss will be recruited. Women with APS and a past history of venous or arterial thrombosis are not eligible for the trial (see below for the full list of exclusion criteria).

The study consists of four periods: screening, baseline and randomization, antenatal follow-up, labour and delivery, and post-partum follow-up.

Eligible and consenting subjects will be assigned to one of two study arms. Randomization is stratified by 'high-risk' or 'non-high risk' laboratory criteria and the timing of pregnancy loss (late loss or no late loss) (section 5.3):

#### Experimental arm

Open-label low-dose aspirin daily from randomization until delivery

#### Standard of care arm

Open-label LMWH prophylaxis until 37 weeks gestation **AND** low-dose aspirin daily until delivery.

The recommended "standard of care" arm is tinzaparin 4,500 IU sc daily until 20 weeks gestation, then tinzaparin 4,500 IU sc twice daily until 37 weeks gestation and aspirin 81 mg po daily until delivery. Treating physicians do have access to other LMWH (dalteparin, enoxaparin) as standard of care, but the suggested regime with tinzaparin is recommended. The use of LMWH prophylaxis beyond 37 weeks gestation and in the 6 week postpartum period will be left up to the discretion of the treating physician.

Each subject will receive education regarding LMWH administration, potential adverse effects and symptoms of VTE by clinic personnel (not research personnel), based on standard of care.

### **Visit Schedule**

#### Screening, Baseline and Randomization

The subject will be evaluated for study eligibility by the investigator or delegated research personnel and once the consent has been assigned, a baseline assessment will be completed. Randomization is done at, or within 7 days of, the baseline visit. The feasibility outcomes will be collected using detailed screening and enrollment logs. Baseline blood work and an obstetrical ultrasound are recommended within 7 days of study enrolment.

#### Antenatal Follow-up

Subjects will attend a clinic visit at  $20 \pm 4$  weeks gestation. All subjects will be monitored for study outcomes and adverse events (AE). Compliance of study medication will be measured at this visit.

#### Labour and Delivery

Study outcomes and AEs will be assessed through a review of subjects' medical records, which may include blood work, urinalysis and ultrasound reports. Data pertaining to the labour and delivery, as well as fetal health at birth will be documented.

#### Postpartum Follow-up

Subjects will attend a clinic visit at 6-12 weeks postpartum. Compliance of study arm during pregnancy will be measured at this visit. All subjects will be monitored for study outcomes and adverse events (AE).

### **Number of Subjects**

The goal recruitment rate is recruitment of 1 subject every 2 months per centre, or a total of 24 patients in 24 months. The primary endpoint is the mean recruitment rate per month.

---

### **Study Population**

#### Inclusion Criteria

Participants must be 18 years or older, have a confirmed pregnancy, and require at least one laboratory criteria and one clinical criteria, as listed below:

Clinical criteria: Past history of pregnancy loss defined as either:

- A. Two or more unexplained pregnancy loss before the 10th week of gestation
- B. One or more unexplained pregnancy loss at or beyond the 10th week of gestation

**AND**

Laboratory Criteria: At least one positive laboratory test listed below that is positive on two or more occasions at least 12 weeks apart\*:

- A. Presence of lupus anticoagulant (LAC)

- B. Anticardiolipin antibody (aCL) of IgG or IgM with a titre > 99th percentile or > 40 GPL or MPL
- C. Anti-β2 glycoprotein antibody of IgG or IgM with a titre > 99th percentile

\*according to the diagnostic criteria of APS, diagnosis should be avoided if more than 5 years is separated between positive antibody testing and a clinical manifestation, such as pregnancy loss

**Exclusion Criteria**

- 1. Greater than 11 weeks +6 days gestational age at time of randomization
- 2. Indication(s) for prophylactic or therapeutic-dose anticoagulation
  - a. Venous thromboembolism (VTE)
  - b. Arterial thromboembolism (ATE)
  - c. Small-vessel thrombosis
  - d. Mechanical heart valve
  - e. Other indication for prophylactic or therapeutic-dose anticoagulation, at the discretion of the treating physician
- 3. Contraindication to heparin or aspirin including:
  - a. History of known heparin or LMWH allergy
  - b. History of known aspirin allergy
  - c. History of HIT
  - d. History of osteoporosis
  - e. Major bleeding within 7 days\*.
  - f. Known thrombocytopenia, based on platelet count < 50 x 10^9/L in the previous 3 months
  - g. Known hepatic disease, based on a medical history of elevated liver enzymes (3x ULN) and/or bilirubin (2xULN) documented within the last 3 months
  - h. Known renal failure, based on Creatinine Clearance < 30 mL/min (Cockcroft Gault) in the previous 3 months
  - i. Known severe hypertension, based on SBP > 200 mmHg and/or DBP > 120 mmHg in the previous 3 months
- 4. Received 7 or more doses of LMWH
- 5. Previous participation in the trial
- 6. Geographic inaccessibility\*\*
- 7. Refused consent

\*All other active or recent bleeding is at the discretion of the treating physician.

\*\*At the discretion of the patient or the treating physician

Please note: Investigators should use caution when prescribing LMWH to patients with a history of gastric ulceration or whom weight >120kg or <45kg.

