### **3.2 Screening, Baseline and Randomization**

Feasibility outcomes will be collected using detailed screening and enrollment logs. Screening logs will document reasons for ineligibility. We will also explore and document reasons for non-consent from patients and local investigators in order to refine the larger multicenter study.

Randomization is done within 7 days of completing the baseline assessment. Subjects who meet the inclusion/exclusion criteria and have signed informed consent will be assigned to one of the two treatment groups (ASA vs LMWH/ASA), stratified by pregnancy loss history and laboratory testing. Details on how a subject is randomized are provided in section 5.3.

Prior to randomization and study entry, a BHCG is needed to confirm the current pregnancy, if not already available. CBC and creatinine blood work will be drawn at baseline, if not previously available within the past 3 months. Past obstetrical history will be recorded.

Subjects can still be enrolled and randomized in the study if they only have one positive antiphospholipid antibody result. A second set of labs would then be drawn 12 weeks apart from the first set, and if the second set is positive they will continue in the study. If the second set is negative, the subject will be withdrawn from the study.

Within 7 days of enrollment, a baseline obstetrical ultrasound is recommended. If the subject is enrolled in early first trimester ( $< 6$  weeks gestation) then the ultrasound will be completed at 6-7 weeks gestation. Blood work will also be drawn on enrollment and stored to be tested in a central laboratory (lupus anticoagulant, anticardiolipin antibody, beta-2 glycoprotein antibody).

Each subject will receive education regarding LMWH administration, potential adverse effects and symptoms of VTE by clinic personnel (not research personnel), based on standard of care.

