### **5.2 Randomization**

Consenting subjects will be randomized up to 7 days after baseline visit. Treatment allocation is determined by central web-randomization. A randomization list has been generated by the trial statistician prior to embarking on the trial. Randomization is in permuted blocks of 10, prepared using random number tables, and is stratified according to laboratory criteria ('High-risk' versus 'Non-high risk' laboratory groups, defined below) and the timing of pregnancy loss (late loss versus no late loss) Any past history of loss  $\geq$  10 weeks gestation will be included in the late loss group.

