**6. MEASUREMENTS AND EVALUATIONS**

**6.1 Demographic and Baseline Characteristics (Baseline Period)**

Subjects will be required to sign a consent form prior to any study procedures being undertaken. During the baseline period, before randomization (up to 11 weeks + 6 days gestation), the following information will be measured and/or recorded:

- Demographic data:
  - Age and birth month
  - Race/Ethnicity

- Height and weight prior to pregnancy
- Current pregnancy data:
  - Gestational age/estimated date of delivery
  - Type of test used to confirm pregnancy and date performed
  - Method of conception
  - Number of fetuses
- Medical history:
  - Presence of SLE diagnosed by rheumatologist or internist
  - Presence of livedo reticularis
  - Presence of hypertension
  - Presence of type 1 diabetes
  - Presence of type 2 diabetes
  - Smoking status
  - Known inherited thrombophilia present and details
- Obstetrical History:
  - Age at start of each pregnancy
  - Gravida, term deliveries, premature deliveries, spontaneous abortions, therapeutic abortions, living children and multiple pregnancies
  - Number, timing and reason of past pregnancy losses
    - According to < 10 weeks, ≥ 10 weeks
  - Past pregnancy complications
    - Pre-eclampsia, SGA, placental abruption, pre-term delivery
  - Treatment of past pregnancies (use of LMWH and/or ASA)

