## **6.2 Laboratory and Imaging Assessments**

A baseline BHCG will be drawn at the screening period, if not already available for the current pregnancy. A CBC and creatinine will be drawn at baseline, if not previously available within the past 3 months. A second set of antiphospholipid labs can be drawn if required to meet the eligibility laboratory criteria, 12 weeks apart from the first set. The subject can be enrolled and randomized to a treatment arm prior to receiving the second set of lab results. According to the diagnostic criteria of APS, diagnosis should be avoided if more than 5 years is separated between positive antibody testing and a clinical manifestation, such as pregnancy loss.

Within 7 days of enrollment, a baseline obstetrical ultrasound is recommended. If the subject is enrolled in early first trimester (<6 weeks gestation) then the ultrasound will be completed at 6-7 weeks gestation. Blood work will also be drawn on enrollment and stored and tested in a central laboratory (lupus anticoagulant, anticardiolipin IgG and IgM antibodies, beta-2 glycoprotein IgG and IgM antibodies).

Additional blood work or imaging assessments will be ordered if an outcome is clinically suspected, and will be left up to the discretion of the treating physician.

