#### **8.1.4. Full Trial Analyses**

Several secondary outcomes will be collected in the pilot trial, which will be included in the analysis of the full trial if there are no significant changes to the trial design.

**Primary analysis:** Analysis will be performed by intention to treat. Intention to treat analysis will be supplemented by a sensitivity analysis that excludes subjects who did not complete the allocated treatment plan. The live birth rate will be compared in the experimental and standard of care arm by an unadjusted Fisher's test of proportions, with 95% confidence intervals provided.

**Secondary analysis:** Analysis will be performed by intention to treat. Intention to treat analysis will be supplemented by a sensitivity analysis that excludes subjects who did not complete the allocated treatment plan. Proportions will be compared between study arms by an unadjusted Fisher's test, with 95% confidence intervals reported. The following outcomes will be analyzed: Pregnancy loss by central laboratory testing, pregnancy loss by gestational age (<10 weeks, 10-19 weeks,  $\geq$ 20 weeks gestation), pre-eclampsia, early onset pre-eclampsia, severe pre-eclampsia, SGA <10th percentile, SGA <5th percentile, SGA <3rd percentile, placental abruption requiring delivery, pre-term delivery <37 weeks gestation, symptomatic VTE, symptomatic ATE, major bleeding, clinically relevant non-major bleeding, non-major non-CRNMB, major peripartum bleeding, minor peripartum bleeding, HIT, symptomatic fracture, allergic reaction, and all-cause mortality.

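### Gestational age at randomisation is recorded and probably prognostic, but the full-trial live-birth analysis does not adjust for it: a small loss of precision, not an error

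*Combined protocol and SAP*

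**What the plan says.** - **Entry window.** The synopsis exclusion criteria, repeated in 4.2, exclude women at "Greater than 11 weeks +6 days gestational age at time of randomization". There is no lower limit beyond a confirmed pregnancy. Sections 3.2 and 6.2 provide for very early entry: "If the subject is enrolled in early first trimester (<6 weeks gestation) then the ultrasound will be completed at 6-7 weeks gestation".
- **Recording.** Section 6.1 lists "Gestational age/estimated date of delivery" among the items collected before randomisation.
- **Stratification.** Section 5.2: "Randomization is in permuted blocks of 10, prepared using random number tables, and is stratified according to laboratory criteria", with a history of late loss as the second factor. That history concerns past pregnancies, so it does not stand in for the week of the current one.
- **Full-trial primary analysis.** Section 8.1.4: "The live birth rate will be compared in the experimental and standard of care arm by an unadjusted Fisher's test of proportions". The secondary outcomes are handled in the same way. The only supplementary analysis excludes women who did not complete their allocated treatment plan.
- **Use of pilot data.** Section 8.1.4 carries pilot outcomes into the full-trial analysis if the design does not change significantly.

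**The concern.** The entry window is about seven weeks wide and covers part of the period in which losses occur. For any one woman under fixed treatment, the chance of live birth, given that she is still pregnant, cannot fall as weeks pass. A woman randomised at 11 weeks has already passed early-loss risk that a woman randomised at 5 weeks still faces. The plan's own outcome bands show this: a woman randomised at 10+0 or later cannot contribute a loss before 10 weeks.

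Entry week is therefore probably prognostic for live birth. Leaving it out of the analysis keeps explainable variation in the error term and leaves the estimate open to chance imbalance in entry week. An analysis stratified only by laboratory group and late-loss history would not remove this. What is at stake is the width of the interval around the full trial's live-birth difference. The pilot's primary outcome, recruitment rate, is not involved.

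**Working it through.** **1. The plan's sample size (8.2).** Inputs: 60% live birth on ASA, a 10-point difference (60% v 70%), 80% power, alpha 0.05 (taken as two-sided), 10% drop-out.

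- Without continuity correction: n = [1.96√(2×0.65×0.35) + 0.842√(0.24+0.21)]² / 0.10² = 356 per arm.
- With continuity correction: (356/4)×[1+√(1+4/(356×0.10))]² = 376 per arm.
- Inflated by 10%: 376×1.1 = 413.6, so 414 per arm, or **828**. The stated figure is reproduced. (Dividing by 0.9 instead gives 836.)

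**2. Precision of the planned comparison.** Evaluable women: 828×0.9 ≈ 745, or 372.5 per arm. The standard error of the difference is √(0.45/372.5) = 0.0348, so the 95% half-width is 1.96×0.0348 = 6.8 points. Unadjusted Wald power is Φ(0.10/0.0348 − 1.96) ≈ 82%.

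**3. Model for entry week (assumptions).** The documents give neither loss risk by week nor the distribution of entry weeks. Assume that entry is uniform over weeks 5 to 12, and that a fraction f of all losses after week 5 occurs evenly before week 12. Let L be the loss risk from week 5. Then

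P(live birth | entry at week g) = (1 − L) / (1 − L·f·(g − 5)/7),

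with L set so that the mean is 60%. The share of outcome variance explained is R² = Var[P(g)] / (0.6×0.4). Adjustment multiplies the variance of the difference by about 1 − R². The equivalent number of women is 828×R². Like-for-like power is Φ(0.10/√(0.45(1−R²)/372.5) − 1.96). The 95% limit on the shift from chance imbalance in entry week is 1.96×√(Var[P(g)]×2/372.5).

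| f | L | Live birth, first to last entrant | R² | Women of 828 | Power gain (points) | Chance shift (points) |
|---|---|---|---|---|---|---|
| 30% | 0.441 | 56% to 64% | 0.25% | 2 | 0.1 | 0.35 |
| 50% | 0.474 | 53% to 69% | 0.9% | 8 | 0.3 | 0.7 |
| 70% | 0.517 | 48% to 76% | 2.5% | 21 | 1.0 | 1.1 |
| 90% | 0.573 | 43% to 88% | 6.7% | 55 | 2.5 | 1.8 |

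The table uses the ASA-arm rate for both arms. At f = 90%, the 70% arm has R² = 5.5%, and the reduction over both arms is 6.1%. Hence the range of 6-7% at the top end.

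**4. Narrower entry.** If entry ran only from week 5 to week 9, the same formulas give R² of 0.2%, 0.5% and 1.0% for f = 50%, 70% and 90%. That is about 2, 4 and 8 women.

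**5. Bias.** Simulations with 372 women per arm and a logistic gradient in entry week gave mean estimated differences of 0.098 to 0.100, with and without adjustment, against a true 0.10.

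**The case against.** The strongest reply is that nothing here is wrong. An unadjusted intention-to-treat comparison of randomised arms is unbiased, and the choice of an adjusted estimator is about efficiency. This stands. Several stronger readings that a reader might infer fail for the same or related reasons:

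- **That chance imbalance in entry week goes uncovered.** It is part of the sampling error that the planned interval already allows for. A shift of 0.35 to 1.8 points lies well inside a half-width of 6.8 points, and it is not an extra error to set against the 10-point MCID.
- **That adjustment raises power from 80-81% to 82-83%.** In simulation (f = 50%, 70%, 90%; 4,000 trials each), Fisher's test had power of 81.1%, 80.0% and 80.4%, an unadjusted Wald test 82.8%, 81.5% and 82.1%, and the adjusted analysis 82.7%, 82.0% and 83.2%. Most of the contrast is Fisher against Wald. Like for like, the changes are −0.1, +0.5 and +1.1 points, within simulation noise of the analytic gains above.
- **That live-birth chance must rise with entry week across the trial population.** This holds for one woman's remaining risk. Women who enter late start allocated treatment later and may differ in loss history, so the documents make a gradient probable but do not establish it.
- **That most of the risk falls inside the window.** The criteria also admit women with a loss at or beyond 10 weeks, and the outcome counts losses at 10-19 weeks and from 20 weeks on. Steeper assumed gradients can give a variance reduction of 12% (98 women), but nothing in the documents supports them.

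The spread of entry weeks may also be narrower than assumed. Women who have had 7 or more doses of LMWH are excluded, and LMWH with ASA is the usual care, so late entry is closed to women already established on it.

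The objection does not remove the case for prespecifying the covariate. It is already collected, and in an open-label trial a covariate added after an imbalance has been seen would look data-driven.

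**Conclusion.** The point holds as a minor one about efficiency in the full-trial analysis. Entry from before 6 weeks to 11+6 weeks, recording before randomisation, absence from the strata and absence from the primary analysis are all confirmed in the text. The loss is about 0.3% to 6-7% of the variance of the live-birth difference, or roughly 2 to 55 of 828 women and 0.1 to 2.5 power points. This rests on uniform entry over 5 to 12 weeks and on 30% to 90% of losses after week 5 falling before week 12. Neither assumption comes from the documents. Earlier-concentrated entry makes the gain smaller, and with no gradient it is nil.

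The documents do not support a claim that the planned comparison is biased, that its interval is invalid, or that 828 is wrong because of this. The pilot's recruitment endpoint is unchanged.

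**What to change.** In 8.1.4, define the primary full-trial estimate as the standardised live-birth risk difference, with a robust 95% CI, from a logistic model containing arm, laboratory risk group, late-loss history and gestational age at randomisation as a continuous term. Include both randomisation factors: a model with arm and entry week alone would leave the strata unadjusted. State that the gestational age used is the value recorded before randomisation. Keep the unadjusted Fisher comparison as supportive.

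The cost is one or two sentences in the analysis section. No new data, no extra women and no change to randomisation or to the pilot endpoints are needed. It is best fixed before pilot outcomes are pooled into the full trial.
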